### **Methods/design:**

#### **Design**

This is a single-center, double-blind, clinical, randomized controlled study. It was approved by Ethical Committee of the Affiliated Hospital of Shandong University of Traditional Chinese Medicine on 15 June 2017 (Approval No. 2017-13th-KY) and registered at the ClinicalTrials.gov (ID. NCT03249701) before recruiting participant. The trail will base on the Consolidated Standards of Reporting Trials (CONSORT 2010) guidelines, and Standards for Reporting Interventions in Controlled Trials of Acupuncture (STRICTA). As the Standard Protocol Items: Recommendations for Interventional Trials (SPIRIT) and corresponding checklist, the participants will be recruited among inpatients who will receive total knee arthroplasty under epidural anesthesia between May 1, 2018 to Oct 1, 2018 at Department of Joint Orthopedics, Affiliated Hospital of Shandong University of Traditional Chinese Medicine, attended by [name]. All potential patients will be identified from operating schedule following the inclusion and exclusion criteria as below, and an appointed researcher will go to the ward for application of selective strategy.

#### **Participants**

All participants will be randomly assigned to experimental group (group E), placebo group (group

P) and control group (group C) at a ratio of 1:1 on the basis of digital random numbers generated by SPSS.17.0 software. For reducing the selection bias, an appointed researcher ([name]) will be responsible for randomization.

### **Study subject**

The study subject is elder inpatient who will be undergoing elective total knee arthroplasty under epidural anesthesia, age from 65 to 85 years old, ASA physical status of I-III, and agree to the informed consent form. The exclusion criteria are the subject (1) refuse to participate in the study; (2) already participate in other clinical studies; (3) is not available due to severe physical status, like ASA classification of IV; (4) required emergency patient; (5) is not suitable to TEAS requirement, e.g. pace maker or metal implant; (6) has deficiency in cognition and literacy and medical history of mental disorder, deep venous thrombosis, or history of drug abuse and acupuncture. Subject should be removed if he/she: (1) switch to general anesthesia; (2) refuses to continuous TEAS administration without any excuse; (3) gets serious adverse reactions in treatment period (e.g. cardiac arrest, comatose); (4) can't accomplish the follow-up visit; (5) acupuncturist changed; (6) low compliance patient.

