### **Outcome Measures**

Primary outcome measure: The primary outcome is the Quality of Recovery-40 questionnaire (QoR-40). It was specifically designed to evaluate quality of recovery in subject after surgery with including five aspects: emotional state, physical comfort, psychological support, physical independence and pain. There are 40 items in total, each adding 1-5 points to the score. Thus, the highest possible score is 200 points; higher scores indicate better quality of recovery. The QoR-40 will be evaluated at preoperative day 1 and postoperative day 1, 3, 7, respectively.

Secondary outcome measures: a. Incidence of postoperative complications: we will assess incidence of postoperative complications when initially find by participant or accompanying family members and diagnosed through examination or scale. Any complication after surgery will be recorded and filled in the case report form. When subject send back to ward, we will require the accompanying family members to record any complaint from subject. Assessment of incidence of postoperative complications will be going on three times and occur at postoperative day 1, 3, 7, respectively. b. The length of hospital stay (LOH): The LOH = the day of patient discharge from hospital – the day of patient admit to hospital, which is calculated base on the Hospital Information System. c. Level of stress response: The Adrenocorticotropic Hormone (ACTH), Cortisol (COR) are chosen to address the level of perioperative stress response. Blood sample taken intravenously and collected at the time of 1 day before surgery (baseline) and 1st day, 3rd day after surgery, respectively. d. Level of inflammatory response: In clinic, the C Reactive Protein and Neutrophil-lymphocyte ratio are well-known to represent the level of perioperative inflammatory response [27, 28]. Blood sample taken intravenously and collected at the time of 1 day before surgery (baseline) and 1st day, 3rd day after surgery, respectively.

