### **Intervention**

Surgical day, the subject will be transferred into operation room and calms down for few minutes with a supine position lying on the surgical bed. Acupoint stimulation administered at 30 min before epidural administration and 30 min after wound closed 2/10 HZ and the intensity adjust to maximal tolerance by participant until end of treatment. The acupuncture points are selected on

the basis of WHO Standard International Acupuncture Nomenclature, and zusanli (ST36, downward 3 inches to the hollow of patellar ligament lateral, Fig.2 a), sanyinjiao (SP6, 3 inches above the top of malleolus medialis, Fig.2 b), neiguan (PC6, 2 inches to the midpoint of wrist skin crease, Fig.2 c), quchi (LI11, the lateral end of the elbow crease when elbow flex 90 degree, Fig.2 d) are located specifically as figure.2 shown. After acupoint area disinfected by 75% alcohol, a medical electrode will be placed on the acupuncture points and connecting to an electro-acupuncture stimulator (SDZ-V, Suzhou medical technology Co. Ltd., Suzhou, China).

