### **Statistical Analysis**

1. Content of statistical analysis: a. Dropout sample: the accuracy numbers lost and dropout rate of subjects are described, and reasons for the dropout is given. b. Balance comparison: The

comparability of subjects in two groups are compared via the baseline information assessing. c. Efficacy analysis: we will treat the QoR-40 as the primary outcome to evaluate the efficacy of TEAS treatment in improving the postoperative recovery after total knee arthroplastic, a mean and deviation as the expression of primary outcome and compared between groups using one-way ANOVA (SNK method), however, before statistic performed, a test of normal distribution of data should be used to determine whether the data are suitable for analysis using the one-way ANOVA. Additional four composite outcome measures (incidence of any postoperative complication, length of hospital stay, level of stress response, level of inflammatory response) are also used as secondary outcomes to determine the efficacy of

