### **Methods of Statistical Analysis**

According to the principle of intention-to-treat (ITT), our data will contain all subjects enrolled. Efficacy and safety measures will be analyzed in accordance with protocol strictly, thus, only subjects who completed the entire trial and followed the protocol requirements should be analyzed. Quantitative and qualitative variables are described statistically with  $X \pm SD$  and count numbers, separately. Quantitative variables will be analyzed by one-way ANOVA (SNK method) in statistic, a normal data distribution needed before performance. Qualitative variables will be analyzed using either  $\chi^2$  test or Fisher' s exact test. All statistical tests are two-sided, and P value  $< 0.05$  will be considered to be statistically significant. Statistical analysis will be performed using SPSS 17.0 software for application.

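### Subjects can be removed for events after randomisation, no outcome collection after removal is provided for, and the analysis is restricted to completers despite an intention-to-treat statement

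*Combined protocol and SAP*

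**What the plan says.** **Study subject.** Six events lead to removal. The first two read: "Subject should be removed if he/she: (1) switch to general anesthesia; (2) refuses to continuous TEAS administration without any excuse". The third is a serious adverse reaction during treatment. The list ends: "can't accomplish the follow-up visit; (5) acupuncturist changed; (6) low compliance patient". The section does not say what the subject is removed from: stimulation, follow-up or the analysis.

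**Intervention.** The timing is "Acupoint stimulation administered at 30 min before epidural administration and 30 min after wound closed". A switch away from the epidural, or a refusal to continue, can therefore come after assignment and after stimulation has begun.

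**Outcome Measures.** "The QoR-40 will be evaluated at preoperative day 1 and postoperative day 1, 3, 7, respectively". Complications are assessed on postoperative days 1, 3 and 7, and bloods are taken at baseline and on days 1 and 3. Length of stay is calculated from the Hospital Information System.

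**Statistical Analysis.** For dropouts the plan is that "the accuracy numbers lost and dropout rate of subjects are described, and reasons for the dropout is given". No outcome follow-up for them and no missing-data method is given.

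**Methods of Statistical Analysis.** One sentence says "According to the principle of intention-to-treat (ITT), our data will contain all subjects enrolled". The next says "only subjects who completed the entire trial and followed the protocol requirements should be analyzed".

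**The concern.** Randomisation makes the arms comparable as assigned. Excluding people for what happens afterwards can undo that, and here several removal reasons could plausibly depend on the arm or on the patient's course.

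The Experimental group and Placebo group sections set current at each patient's maximal tolerance, while the Control group section provides electrodes without actual current. Refusal because the current is uncomfortable can arise in groups E and P but hardly in group C. Serious reactions mark a difficult perioperative course, and a switch to general anesthesia may do so too. QoR-40 covers pain, physical comfort and emotional state, so it is likely to be lower in such patients. If more of them are taken out of one arm, that arm looks better than it is.

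Two gaps combine. A site that takes removal to mean leaving the study has no instruction to give the day 1, 3 and 7 questionnaires or take the scheduled bloods, and these cannot be obtained later. Even where the data are collected, the completer sentence excludes these subjects from the analysis. Repairing only one of the two places leaves the problem standing.

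**Working it through.** **1. The plan's own figures.** From Sample Size Calculation: z-values 1.96 and 1.282, means 176.9 and 164.3 (difference 12.6), SDs 11.1 and 13.7.

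n = (1.96 + 1.282)² × (11.1² + 13.7²) / 12.6² = 10.51 × 310.90 / 158.76 = 20.58, rounded up to 21. Adding 20%: 21 × 1.2 = 25.2, rounded up to 26. Both stated figures reproduce.

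If removals use the whole allowance equally in each arm, 0.20 × 26 = 5.2. About 5 per arm are lost and about 21 remain, which is the number the formula asked for. Equal removal is therefore covered for precision. The question is unequal removal.

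**2. Simple bias formula.** For an arm with removal rate r, completer mean minus mean of all randomised = r × (completer mean − removed mean). With the same gap in both arms:

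bias in the difference = (r₁ − r₂) × gap.

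Rates and gaps are assumptions; the document gives none.

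| Removed | Gap 5 points | Gap 13.7 points |
|---|---|---|
| 20% vs 10% | 0.10 × 5 = 0.5 | 0.10 × 13.7 = 1.4 |
| 20% vs 5% | 0.15 × 5 = 0.75 | 0.15 × 13.7 = 2.1 |
| 20% vs 20% | 0 | 0 |

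**3. Effect on the false-positive rate.** Assume no true effect, 26 per arm, one pairwise comparison, SD = √((11.1² + 13.7²)/2) = 12.47, and a normal removal propensity with correlation ρ to poor QoR-40. Removing the top fraction r raises the completer mean by ρ × SD × φ(z)/(1 − r), where z is the normal quantile at 1 − r and φ is the normal density.

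- r = 20%: 0.280/0.80 = 0.350
- r = 5%: 0.103/0.95 = 0.109
- Bias for 20% vs 5%: ρ × 12.47 × (0.350 − 0.109) = ρ × 3.01

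The two-sided type I error of a t test on the retained patients comes from simulation:

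| ρ | Spurious difference, 20% vs 5% | Type I error (nominal 5%) |
|---|---|---|
| 0.2 | 0.6 points | about 5.5% |
| 0.5 | 1.5 points | about 7% |
| 0.8 | 2.4 points | about 10.5% |

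With 10% vs 5% and ρ = 0.5, the bias is about 0.5 points and the error stays near 5%. With 20% in both arms and the same ρ, the bias is zero.

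As a check on plausibility, at 20% removal ρ = 0.5 implies that removed patients score about 10.9 points below completers, and ρ = 0.8 about 17.5 points. The latter exceeds the planned 12.6-point effect, so ρ = 0.8 is a severe case.

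**The case against.** A reader might infer that data collection stops at removal, so that the intention-to-treat data will not exist and no choice of analysis population could help. The document does not support that. Removal has no stated object, and exclusion from the analysis set is at least as natural a reading: being unable to complete follow-up is itself on the list, which is circular as a rule for ending follow-up but sensible as an analysis exclusion. On that reading the main defect is the contradiction in Methods of Statistical Analysis, and settling it for intention-to-treat would largely cure it. What can be said is that no provision is made to collect outcomes after removal.

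Nor would every outcome be lost. Length of stay remains obtainable from the Hospital Information System, complications are to be recorded with no stated exception for removed subjects, and reasons for dropout are already required.

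A reader might also infer that the comparison is certain to be biased. It is not. The 20% allowance covers all dropout and applies to every group alike, which is the no-bias case when selection is also alike; placing it in one arm is an assumption. Stimulation is confined to the surgical day, which limits the opportunity for refusal. Whether a switch to general anesthesia depends on the arm is conjecture. Under mild assumptions the bias is small against 12.6 points.

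These objections limit the strength of the claim but do not remove it. On either reading of removal, following the plan as written analyses a set selected after randomisation while claiming intention-to-treat.

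**Conclusion.** The point holds as a gap in provision together with a contradiction in the analysis set. It is not a finding that data collection stops or that bias is certain. Removal reasons 1, 2, 3, 5 and 6 can arise after randomisation, outcomes after removal are not provided for, and the completer sentence conflicts with the intention-to-treat sentence.

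Under an assumed 20% versus 5% removal and no true effect, the spurious QoR-40 difference is about 0.6 to 2.4 points, with type I error about 5.5% to 10.5%, for correlations of 0.2 to 0.8. That is well below the planned 12.6 points, but at the upper end the false-positive rate is about doubled. The rates and correlations are not in the document, and the bias vanishes if removal and selection are equal across arms. The point should be settled before recruitment, because a postoperative questionnaire or blood sample not taken on its day cannot be recovered.

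**What to change.** **Study subject.** Replace the single removal list with two categories:

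- (a) The subject stops or does not complete assigned stimulation, or has another protocol deviation (items 1, 2, 3, 5 and 6). These subjects stay in the study, with QoR-40, complications, bloods and length of stay collected on the existing schedule where the patient is able. A comatose patient, for example, cannot complete a questionnaire, and that value is then missing.
- (b) The subject withdraws consent to follow-up. Only this ends data collection.

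Treat a missed visit (item 4) as missing data, not as a reason for removal. Record the date and category alongside the reason already required.

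**Methods of Statistical Analysis.** Make the analysis of all randomised subjects by assigned group primary, with a stated missing-data method. Keep the completer analysis as a sensitivity analysis.

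The rules for when stimulation is stopped are not changed, and the sample size formula is unaffected.

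**Cost.** Protocol wording, a case report form field, and a few more assessments on the schedule already planned. The estimate will include patients with incomplete stimulation and may be slightly diluted.

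### Removing a subject who misses the follow-up visit, together with a completer-only analysis that conflicts with the intention-to-treat sentence, would discard usable data and could make retention depend on outcome

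*Combined protocol and SAP*

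**What the plan says.** All references are to the combined protocol and SAP.

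- **Study subject.** A list of removal reasons is introduced by "Subject should be removed if he/she", and the fourth is "4) can't accomplish the follow-up visit". The visit is singular and tied to no day. The text does not say whether removal means stopping treatment, leaving follow-up or exclusion from analysis.
- **Methods of Statistical Analysis.** One sentence invokes intention-to-treat and states that "our data will contain all subjects enrolled". The next, on efficacy and safety, states that "only subjects who completed the entire trial and followed the protocol requirements should be analyzed". The two are not reconciled.
- **Outcome Measures.** For the primary outcome, "The QoR-40 will be evaluated at preoperative day 1 and postoperative day 1, 3, 7, respectively". Complications are assessed on postoperative days 1, 3 and 7. Blood samples for stress and inflammation are taken at "1 day before surgery (baseline) and 1st day, 3rd day after surgery, respectively". Length of hospital stay is a secondary outcome, "which is calculated base on the Hospital Information System".
- **Statistical Analysis.** Dropouts are to be counted and their reasons given. No method for missing data is named.
- **Sample Size Calculation.** 21 per group, raised to 26 for 20% dropout.

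**The concern.** The removal rule acts on the subject, while what is missing is one visit's values. The completer-only sentence then carries the removal into the analysis. Day 7 is the last scheduled assessment, so it is the natural reading of the undefined visit. On that reading, a single missed day takes out measurements that were already complete or that never needed a visit.

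Selection is the second issue. Completing day 7 is a post-randomisation event. A patient may miss it because of early discharge or because of being too ill to answer. Discharge date defines one secondary outcome, and illness bears on QoR-40 and complications. If either drives the missed visit, the groups compared are no longer the groups randomised. The 20% inflation replaces lost numbers; it does not correct selection.

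**Working it through.** **1. What a subject missing only day 7 already has**

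| Outcome | Schedule or source | In hand without day 7 |
|---|---|---|
| QoR-40 | baseline, days 1, 3, 7 | baseline and two of three postoperative scores |
| Complications | days 1, 3, 7 | two of three assessments |
| ACTH, cortisol, CRP, neutrophil-lymphocyte ratio | baseline, days 1, 3 | all |
| Length of stay | Hospital Information System | yes, once discharged |

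The completer-only sentence excludes all of this from the efficacy analysis. The intention-to-treat sentence keeps it.

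**2. The plan's own allowance for loss**

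Inputs from Sample Size Calculation: 176.9 (SD 11.1) and 164.3 (SD 13.7), difference 12.6, z-values 1.96 and 1.282.

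n = (1.96 + 1.282)² × (11.1² + 13.7²) / 12.6² = 20.58, so 21 per group, as stated. 21 × 1.2 = 25.2, so 26, as stated. The plan therefore allows for losing 26 − 21 = 5 per group.

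**3. Ceiling on lost precision**

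Interval width scales with 1/√n: √(26/21) = 1.11, so about 11% wider with 21 analysed than with 26. This charges every planned dropout to criterion (4). Five other removal reasons share that allowance, so 11% is an upper bound within planned dropout.

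**4. Possible bias in length of stay (illustration)**

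Assumptions not in the documents: postoperative stay is normal with SD 2 days; a fraction q of those discharged before day 7 miss the visit and are removed; time from admission to surgery is alike in the groups, so it cancels from the difference.

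For a group with mean μ, let a = (7 − μ)/2. The fraction removed is qΦ(a), and the mean stay of those retained is μ + 2qφ(a)/(1 − qΦ(a)).

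For means of 8 (control) and 7 (experimental) with q = 0.5:

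- Control: a = −0.5, Φ = 0.3085, φ = 0.3521. Removed 15%; retained mean 8 + 0.3521/0.8457 = 8.416.
- Experimental: a = 0, Φ = 0.5, φ = 0.3989. Removed 25%; retained mean 7 + 0.3989/0.75 = 7.532.
- Difference 8.416 − 7.532 = 0.88 day, against a true 1.0.

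The same formula for other inputs, true difference 1.0 except in the last row:

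| Assumed means (control, experimental) | q = 0.5 | q = 1 |
|---|---|---|
| 8, 7 | 0.88 | 0.42 |
| 10, 9 | 0.87 | 0.70 |
| 12, 11 | 0.96 | 0.92 |
| 8, 8 (no effect on stay) | 0 | 0 |

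The 0.42 cell removes 31% of control and 50% of experimental subjects, well above the planned 20%. The 0.88 cell removes 15% and 25%, about 20% on average, which would use the whole dropout allowance.

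**5. Possible bias in QoR-40 (illustration)**

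Assumptions not in the documents: 25% of controls leave before the visit; treatment shortens stay by 0.5 SD; QoR-40 and stay correlate at −0.3 to −0.5; 20% to 80% of early leavers are removed. Removal then runs from 5% (control) and 8.6% (experimental) to 20% and 34.5%. The planning difference of 12.6 falls to between 12.5 and 11.6. If treatment does not change stay, loss is balanced and the difference stays at 12.6 apart from simulation noise.

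**The case against.** The strongest reply is that the plan never plainly orders these data to be discarded. The Study subject section does not define removal, the follow-up visit is not named as day 7, and the intention-to-treat sentence would keep everyone. This stands as far as it goes: exclusion follows one of two conflicting instructions and one reading of an undefined visit. It does not clear the plan, because the completer-only sentence is the one that names efficacy and safety, and it agrees with the removal list.

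It can also be said that the bias is conjectural. That stands too. A reader might infer that early leavers will be lost and the effect on stay roughly halved. The documents do not support this: they do not say whether day 7 is done on the ward, at a return visit or by telephone, and they give no expected stay. Nor is the direction settled. The illustrations model early leavers only, and loss of patients too ill to be assessed could add to or offset that effect, depending on which group they come from.

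Finally, the plan already inflates for dropout. That protects the number analysed, not comparability.

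**Conclusion.** The point holds in conditional form. Criterion (4) and the completer-only sentence, followed as written, exclude a subject for an incomplete follow-up, against the intention-to-treat sentence beside it. If the visit means or includes day 7, complete blood data, two postoperative QoR-40 scores, two complication assessments and a known length of stay are lost for no stated reason.

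The size and direction of any bias cannot be fixed from the documents. Under the assumed stays it is nil if treatment does not change stay, modest in the half-missing cases (1.0 day falls to between 0.87 and 0.96), and larger if more miss the visit. The assumed QoR-40 case shows a small to moderate attenuation.

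A reader might also take the 11% as the cost of this criterion. The documents do not support that, since the planned dropout covers every removal reason; it is a ceiling.

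**What to change.** 1. In Study subject, delete criterion (4) as a reason for removal, and state that a missed visit makes only that visit's values missing.
2. In Methods of Statistical Analysis, replace the completer-only sentence: the main analysis includes every randomised subject in the assigned group with all data collected, and any completer analysis is supportive only. Step 1 alone would not work, because the completer-only sentence would still exclude these subjects.
3. Take length of stay from the Hospital Information System for every randomised subject.
4. Analyse QoR-40 with a method that uses the available visits, for example a repeated-measures mixed model adjusted for baseline, with a sensitivity analysis for missing day 7.
5. For subjects discharged before day 7, have the existing data collector obtain the day 7 QoR-40 and complication questions by telephone, in the same way in all groups, and record the mode.

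The cost is revised wording, a somewhat fuller analysis and some telephone calls. The small downside is mixed mode of assessment at day 7. These changes concern keeping data in the analysis, not when treatment stops.
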